# Aim and Hypothesis

The primary aim of this study is to conduct a three-group randomized, intervention trial to measure the effectiveness of the values-framed individually tailored messaging Vaccines and Your Baby (VAYB) intervention. The primary hypothesis to be tested is that infants of mothers who receive the VAYB intervention will be more up to date on vaccination and mothers will have lower levels of vaccine hesitancy than those receiving an untailored version of the intervention or those receiving usual care. A secondary aim of the project is to assess the impact of the intervention on vaccination attitudes.

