#### Randomization

Participants are randomized using stratified randomization along with permuted block technique using a 1:1:1 allocation ratio between the VAYB, untailored and usual care arms. Randomization occurs using software embedded in the study website immediately following enrollment into the study. Randomization remains in place throughout the study. Participants are first stratified into either a hesitant or non-hesitant group, based on vaccine hesitancy status from the baseline questionnaire. Hesitancy status is assessed using a 5-item validated measure developed by Opel DJ (olejado). Participants are categorized based on the measure's suggested (but unpublished) cutoffs. Participants from each group are then added to their own set of blocks that each contain 6 slots. There are 2 slots available for each of the 3 study arms. These slots are randomly ordered when the block is created. When all 6 slots are filled, a new block with 6 randomly ordered slots is added.

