# 2. Vaccination attitudes and hesitancy

Vaccine attitudes and hesitancy was in a questionnaire online. These data are used to assess changes over time in vaccination attitudes and hesitancy, and how these relate to study arm, vaccination values, and vaccination status. Vaccination attitudes are assessed using measures previously developed by our team and others. vaccine values are assessed using a novel framework we have developed, and vaccine hesitancy is assessed using a 5-item validated measure (Olejado). A variety of covariates and potential moderators will be assessed as part of this analysis including parent age, gender and insurance coverage type (such as Medicaid and HMO), and mother's age, race, and ethnicity. Also included will be metrics measuring website engagement (VAYB and Untailored arms only) including time spent on the website, number of times viewing website, number and order of pages viewed, and match between stated concerns and website material viewed (VAYB arm only).

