# **Analysis**

Total days undervaccinated will be analyzed in two ways. First it will be done using a dichotomous variable (up-to-date vaccination status). Second analysis will be done as a continuous measure. The dichotomous variable will be analyzed using logistic regression to estimate odds ratios and associated 95% confidence intervals. We will use a nonparametric analysis and a rank transformation approach to assess the continuous measure as total days undervaccinated has a highly skewed distribution. We will use a modified intention to treat framework. To ensure vaccination data available for assessment of outcomes, this analytic cohort will include infants of all randomized mothers who maintained KPCO health coverage for the allotted amount of time (200 days for the primary outcome, 489 days for the secondary outcome) with no more than 90 days of no coverage. For both vaccination behavior measures, if a statistically significant association is observed in the primary analysis, we will conduct analyses stratified by baseline vaccine hesitancy as measured by the 5-item vaccine hesitancy scale described above (Olejado).

For survey measures, we will assess changes in vaccine attitudes and intention over time. All survey items are measured using Likert scales and will be analyzed as linear measures. For each survey outcome average change over time by arm will be assessed using a repeated measures ANOVA. Mixed linear models will be used to assess the "difference in difference" over time in these means, by arm, controlling for the covariates. To ensure survey outcomes for analysis, we will use a modified intention to treat analysis that includes all participants with data from at least one non-baseline questionnaire.

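### Survey outcomes: the arm contrast is specified only as an average over the hesitancy strata used for randomisation, and the stratum is not named as a covariate or moderator

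*Combined protocol and SAP*

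**What the plan says.** **Randomisation.** The Randomization section states: "Participants are first stratified into either a hesitant or non-hesitant group, based on vaccine hesitancy status from the baseline questionnaire". Allocation within each stratum is in blocks of six, "using a 1:1:1 allocation ratio between the VAYB, untailored and usual care arms".

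**Hypothesis.** The Aim and Hypothesis section pairs vaccination with hesitancy: it expects that in the VAYB arm "mothers will have lower levels of vaccine hesitancy than those receiving an untailored version of the intervention or those receiving usual care". The effect on attitudes is a secondary aim.

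**Vaccination measures.** The Analysis section provides for analyses stratified by baseline hesitancy, with this scope and condition: "For both vaccination behavior measures, if a statistically significant association is observed in the primary analysis".

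**Survey measures.** The same section gives two analyses. The first is: "For each survey outcome average change over time by arm will be assessed using a repeated measures ANOVA". The second is a mixed linear model for the difference in difference "over time in these means, by arm, controlling for the covariates". Neither is accompanied by a stratum-specific estimate or an arm-by-stratum interaction.

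**Covariates and moderators.** The secondary-outcome section on attitudes and hesitancy says that several covariates and potential moderators will be assessed. It names age, gender, insurance type, race, ethnicity and website engagement. It also relates changes to arm, vaccination values and vaccination status. The list is worded as examples, so it is open, but the randomisation stratum is not on it.

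**The concern.** The sponsor treats baseline hesitancy as important enough to stratify the randomisation by it, and as the one subgroup variable for the vaccination measures. It is equally plausible as a modifier of the effect on hesitancy and attitudes, yet there the plan does not name it.

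Two things could follow if the effect differs by stratum. First, a reduction confined to hesitant mothers would be averaged with mothers who did not change, and the trial might report no effect on hesitancy or attitudes. Second, a fall in one stratum and a rise in the other could offset each other in the overall mean. In either case the authors could still look within strata after seeing the data, but the result would be post hoc. Adjusting for covariates does not remove the problem: even with the stratum as a covariate, the model returns one common arm effect.

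**Working it through.** **No figure to reproduce.** The documents state no sample size, power, effect size, SD or hesitant share. Every input below is an assumption chosen for illustration.

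**Inputs.** n = 300 mothers per arm; hesitant share h; fall of d = 1 point in hesitant mothers and x points in the others (x = 0 at first); SD of change σh = 2.0 (hesitant) and σn = 1.2 (non-hesitant); normal approximation, two-sided 5%, one pairwise arm contrast.

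**Formulas.**
- Overall: difference h·d + (1−h)·x; SE = √[2(h·σh² + (1−h)·σn²)/n]. This uses within-stratum variance only, so it treats the overall contrast as stratum-adjusted.
- Within hesitant: difference d; SE = √[2σh²/(n·h)].
- Interaction: difference d − x; SE = √[2σh²/(n·h) + 2σn²/(n(1−h))].

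**Worked case, h = 0.20, x = 0.**
- Overall: difference 0.20; SE = √[2(0.8 + 1.152)/300] = 0.114; z = 1.75; power 42%.
- Within hesitant: difference 1.0; SE = √(8/60) = 0.365; z = 2.74; power 78%.
- Interaction: SE = √(8/60 + 2.88/240) = 0.381; z = 2.62; power 75%.

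**Range over the assumed share (x = 0).**

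| h | Overall difference | Power, overall | Power, within hesitant | Power, interaction |
|---|---|---|---|---|
| 10% | 0.10 | 16% | 49% | 48% |
| 20% | 0.20 | 42% | 78% | 75% |
| 25% | 0.25 | 57% | 87% | 83% |

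The ordering is the same with 200 or 400 per arm. With x = 0 it does not depend on the SDs either: the overall z exceeds the within-stratum z only if h·σh² > h·σh² + (1−h)·σn², which cannot happen.

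**A second set of assumptions.** With 200 per arm, h = 0.20 and an effect of 0.5 SD in hesitant mothers only, power is 17% overall and 61% within the stratum. If the SD in non-hesitant mothers is half as large, overall power rises to 35%.

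**Dropping x = 0.** The two contrasts have equal power when [h·d + (1−h)·x]/SE(overall) = d/SE(within). At h = 0.20 this gives x = (0.114/0.365 − 0.20)/0.80 ≈ 0.14. Across shares of 10% to 25%, x is 0.12 to 0.15. At h = 0.20:
- x = 0.25: overall 94%, within hesitant 78%.
- A uniform fall of 0.5 points: overall 99%, within hesitant 28%.

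**Opposite shifts.** The overall difference is zero when non-hesitant mothers rise by d·h/(1−h), which is 0.25 points at h = 0.20. A rise of 0.5 points in non-hesitant mothers with no change in the others gives an overall difference of 0.40, z = 0.40/0.114 = 3.51, power 94%.

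**The case against.** The strongest case against is that the planned contrast already answers the stated question. The hypothesis is about mothers, not hesitant mothers. The whole-arm difference is a valid estimate of the average effect, and stratified randomisation does not oblige anyone to report subgroup effects for every secondary outcome. This stands, and it is why the point is an improvement and not an error.

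Four stronger readings are tempting, and the documents do not support them.

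- *That the stratum could never enter the survey analysis.* The moderator list is open. The accurate statement is that the stratum is not named.
- *That non-hesitant mothers can only stay put or rise.* Being below a cutoff is not being at the floor. The cutoffs are described as unpublished, and no score range or baseline distribution is given. Nothing points to a floor or ceiling for attitudes or intention.
- *That the overall contrast is the weakest one.* This holds when only hesitant mothers respond. A modest fall in the others reverses it.
- *That a rise among non-hesitant mothers would go unseen.* At the assumed shares they are 75% to 90% of the sample and dominate the average. Such a rise is masked only if the hesitant stratum offsets it.

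The objection on volume also has weight. Three outcome families, two arm contrasts, two strata and up to three follow-ups give up to 3 × 2 × 2 × 3 = 36 estimates, more if attitudes comprise several measures. These should therefore be presented as estimates without claims of significance.

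**Conclusion.** The point holds as a low-cost improvement to the pre-specification. The plan randomises by hesitancy stratum and analyses vaccination by it, but for the survey outcomes it specifies only arm contrasts averaged over the strata and does not name the stratum as covariate or moderator. The overall contrast remains valid for the hypothesis as worded; a reader should not infer that it is biased or that it fails to address the aim.

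The risk is conditional on the effect differing by stratum. Its size (power of 42% against 78% in the worked case) rests wholly on assumed values for sample size, share, SDs and effect, and on no effect in non-hesitant mothers. Since neither contrast is better in every scenario, both should be reported.

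**What to change.** In the Analysis section, for the hesitancy, attitude and intention scores:

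1. Include the randomisation stratum as a covariate in the mixed linear models, and keep the overall arm contrast as the main result.
2. Add an arm-by-time-by-stratum term with its lower-order terms. Report VAYB v untailored and VAYB v usual care within each stratum, with 95% CIs and the interaction estimate, whatever the overall result. Label these as pre-specified secondary results, focused on estimation and without significance claims.
3. Make the comparison between arms within stratum, not change from baseline within an arm, because regression to the mean will move scores in the hesitant stratum in every arm.
4. For the hesitancy score, use the 10-12 and 13-15 month surveys. The description of the 4-6 month survey can be read as omitting two of the five hesitancy items, so the full score may not exist at that time.

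The cost is a short addition to the text and extra model terms. The stratum is known for every randomised mother, so no new data are needed. The downside is more estimates to report, with wide intervals if the hesitant stratum is small.

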# Missing data

Nearly all vaccines provided to KPCO patients are documented in the EMR, and doses provided outside KPCO are documented in Colorado Immunization Information System (CIIS). Therefore, we expect minimal missing data for vaccination outcomes. To ensure the most complete record, CIIS will be cross checked for all participants to identify any vaccine doses given to infants outside the KPCO system that are missing from the KPCO EMR. Participants who do not have vaccination data present in either system will be assumed to have not gotten a vaccine dose elsewhere.

For survey data, due to our recruitment strategy, we anticipate no missing data at baseline, as completion of the baseline survey was a criterion study enrollment. However, there may be missing data for subsequent surveys as completion of the subsequent surveys was not required to remain in the study. For missing data in surveys beyond baseline, multiple imputation models will be developed for analyses involving multiple survey points where greater than 10% of subjects would be lost due to missing values.

#### **Ethics and Dissemination**

# Approvals

This study is approved by the Institutional Review Boards at the University of Colorado and KPCO.

#### **Funding**

This work was funded by the National Institutes of Health, Eunice Kennedy Shriver National Institute of Child Health and Human Development, # R01HD079457.

# Competing Interests

[name] serves on Advisory Boards for Merck, Pfizer and Sanofi Pasteur, and has provided consulting services to Pfizer. She does not receive any research funding from these companies. All other authors have no competing interests to declare.

